16.2 Sample Size Justification

The primary aim of this study is to ensure that the toxicity rate (defined as chest wall pain greater than or equal to grade 3, or painful/symptomatic brachial plexopathy and acute symptomatic pneumonitis greater than or equal to grade 3) from hypofractionated post-mastectomy radiation is controlled at an acceptable level. The current toxicity rate from standard regimens is approximately 3%. We need to ensure that the rate from the hypofractionated scheme is as low as possible, and specifically that it is below 9% with 80% power, using a 10% level one-sided test of proportions. To meet this requirement, we will need to accrue 67 patients. If there are 5 or more toxicity events among 67 patients, we reject the hypothesis that the rate is 3%. The exact significance level of this discrete variable test is 0.0508, and the exact power is 0.732.

Early stopping: The study will be stopped early if, at any time, we are more than 80% sure that the toxicity rate exceeds 9%. For example, if we have 4 patients experiencing a toxicity event out of the first 33 patients enrolled, we will stop the trial. But if there are only 3 patients with toxicity, the trial would continue. As mentioned above, if five patients show unacceptable toxicities, the trial will end, even if this happens before the full 67 patients have been accrued. This stopping rule table consists of posterior probabilities that the true toxicity level exceeds 9%, assuming a uniform prior on a binomial distribution.

		k: Number of unacceptable toxicities				
		0	1	2	3	4
1	0.8281	0.9919				
2	0.753571	0.977158	0.999271			
3	0.68575	0.957035	0.997281	0.999934		
4	0.624032	0.932619	0.993659	0.999696	0.999994	
5	0.567869	0.904847	0.988165	0.999152	0.999967	
6	0.516761	0.874519	0.980667	0.998463	0.999894	
7	0.470253	0.84232	0.971113	0.996589	0.999738	
8	0.42793	0.808834	0.959522	0.994296	0.999455	
9	0.389416	0.774553	0.94596	0.991166	0.99899	
10	0.354369	0.739891	0.930533	0.987098	0.998286	
11	0.322475	0.705194	0.915376	0.982007	0.997279	
12	0.293453	0.670749	0.894639	0.97583	0.995905	
13	0.267042	0.636792	0.874489	0.968523	0.994098	
14	0.243008	0.603515	0.853096	0.96006	0.991796	
15	0.221137	0.571069	0.830634	0.950433	0.98894	
16	0.201235	0.539575	0.807273	0.939651	0.985474	
17	0.183124	0.509125	0.78318	0.927737	0.98135	
18	0.166643	0.479785	0.758515	0.914727	0.976525	
19	0.151645	0.451602	0.73343	0.900668	0.970963	
20	0.137997	0.424606	0.708065	0.885617	0.964637	

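### Read literally, the 80% posterior stopping rule in Section 16.2 ends the trial at patient 1 whatever happens to her; it needs a minimum-event clause and operating characteristics of its own

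*Combined protocol and SAP*

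**What the plan says.** Everything visible on this point is in Section 16.2 (Sample Size Justification).

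- **Trigger.** "The study will be stopped early if, at any time, we are more than 80% sure that the toxicity rate exceeds 9" per cent.
- **Table.** It is said to hold "posterior probabilities that the true toxicity level exceeds 9%, assuming a uniform prior on a binomial distribution". It covers 1 to 35 patients and 0 to 4 events. Row 1 reads 0.8281 for no toxicity and 0.9919 for one.
- **Worked example.** "if we have 4 patients experiencing a toxicity event out of the first 33 patients enrolled, we will stop the trial". With 3 events at that same point, accrual goes on.
- **Cap.** Separately, "if five patients show unacceptable toxicities, the trial will end, even if this happens before the full 67 patients have been accrued".
- **Fixed test.** "The current toxicity rate from standard regimens is approximately 3" per cent. The aim is to show of the new schedule "specifically that it is below 9% with 80% power, using a 10% level one-sided test of proportions". The plan rejects 3% if 5 or more of 67 patients have an event, with exact significance level 0.0508 and exact power 0.732.

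Section 16.2 states no run-in and no minimum number of patients or events before the posterior rule applies. Section 14 (Data and Safety Monitoring) is redacted, and Section 16.2 does not refer to it.

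**The concern.** A posterior stopping rule should respond to patients' outcomes. Here the uniform prior alone already satisfies the criterion, and one patient without toxicity is not enough to bring the probability below the threshold. The first application of the rule therefore gives the same answer whatever happens to that patient.

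Nobody is likely to close the trial because the first patient did well. But to carry on, the investigators must set aside a pre-specified rule at its first use, and the plan does not say which other cells may be set aside. That matters because neighbouring cells are real decisions: one event among the first 8 patients also crosses the line. Toxicity is the primary aim in Section 16.2, and the only error rates quoted there are for a single test at 67 patients, not for a rule applied at any time.

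**Working it through.** **Inputs, all from Section 16.2.** Uniform prior, which is Beta(1, 1); binomial events; stop if P(rate > 0.09) > 0.80; five events end the trial; 67 patients; reference rates 3% and 9%.

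**1. Reproduce the plan's figures.** After k events in n patients the posterior is Beta(1 + k, 1 + n − k).
- n = 1, k = 0: Beta(1, 2), so P(rate > 0.09) = 0.91² = 0.8281. Printed: 0.8281.
- n = 1, k = 1: Beta(2, 1), so 1 − 0.09² = 0.9919. Printed: 0.9919.
- n = 33, k = 4: 0.813, above 0.80 (stop). n = 33, k = 3: 0.633, below (continue). Both match the table and the worked example, so table and threshold are used together as described.
- Fixed test: P(5 or more of 67) is 0.0508 at 3% and 0.7316 at 9%, matching the stated 0.0508 and 0.732.

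All other cells agree except two small differences (n = 6, k = 3: printed 0.998463, computed 0.998163; n = 11, k = 2: printed 0.915376, computed 0.913376). Neither is near 0.80.

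**2. Apply the rule at the start.**
- No patients: 1 − 0.09 = 0.91.
- One patient: 0.8281 or 0.9919. Both exceed 0.80, so the probability of stopping at n = 1 is 1 at any true rate.
- Two patients, no events: 0.91³ = 0.7536, below 0.80. With no events, n = 1 is the only row that triggers.

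**3. Where the rule triggers once events occur.**

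| Events | Last n at which the posterior exceeds 0.80 |
|---|---|
| 1 | 8 |
| 2 | 16 |
| 3 | 24 |
| 4 | 33 |
| 5 | any n, by the cap |

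For example, at n = 8, k = 1: 0.91⁹ + 9 × 0.09 × 0.91⁸ = 0.4279 + 0.3809 = 0.8088, and at n = 9 the printed value is 0.7746.

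**4. Chance of stopping.** Among trials still running, P(n, k) = P(n − 1, k)(1 − p) + P(n − 1, k − 1)p, for n = 1 to 67. States that meet the rule or reach five events are removed and added up.

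| Rule (five-event cap always in force) | True rate 3% | True rate 9% |
|---|---|---|
| As worded | 100% | 100% |
| Posterior rule only after at least 1 event | 25.8% | 83.6% |
| Posterior rule only after at least 2 events | 11.9% | 78.3% |
| Fixed 5-of-67 test alone | 5.1% | 73.2% |

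In the second row at 3%, most of the 25.8% comes from a first event within the first 8 patients: 1 − 0.97⁸ = 21.6%.

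**The case against.** The best defence is that the intention is plain. The table counts unacceptable toxicities, both worked cases involve events, and the zero-event trigger disappears once a second patient is counted. On that view this is a missing clause that no monitoring team would trip over. This is fair as to the likely practical effect, and it confines the zero-event fault to one cell. It does not supply the clause: the wording allows stopping at any time, and the offending value is in the plan's own table.

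A provision in the redacted Section 14 cannot be excluded. If one exists, Section 16.2 should point to it.

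A reader might infer more than the documents support:
- **That this is the trial's only safeguard against toxicity.** It is not. The five-event cap does not depend on the prior, and Sections 7.10.5 and 10 contain patient-level provisions.
- **That the uniform prior contradicts the 3% rate.** The 3% is for standard regimens and the prior is for an untested schedule. Not borrowing the standard rate is a cautious choice, even though it lets the prior dominate the first decisions.
- **That the prior must be replaced.** A prior such as Beta(0.9, 9.1) removes stopping on 0 or 1 events but loosens every boundary: the last stopping n falls from 16 to 7 for two events, 24 to 16 for three and 33 to 24 for four. It would reverse the plan's own 4-of-33 example. Compared with the one-event clause, it cuts stopping at a true 9% from 83.6% to 74.5% and raises mean enrolment at 9% from about 25 to 44 patients. It is a trade-off, not a correction.

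**Conclusion.** The point holds in this form: as worded, the posterior rule stops every trial at patient 1, so it cannot be followed literally. The arithmetic in the table's first row is right; the fault is that the rule has no minimum-event or minimum-patient condition. The zero-event trigger is limited to n = 1.

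The second consequence is larger in practice. Once the zero-event trigger is removed, the rule with its cap stops 25.8% of trials at a true 3% and 83.6% at a true 9%, so the quoted 0.0508 and 0.732 do not describe the trial with this rule in force. These figures assume a look after every patient, each patient's outcome known before the next look, independent events at a constant rate, and the same posterior calculation continued past the last printed row to n = 67. The conclusion about patient 1 rests only on the printed table and the 80% threshold.

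**What to change.** In Section 16.2:
1. Add one sentence: the posterior rule applies only once at least one unacceptable toxicity has occurred. Keep the five-event cap and the 4-of-33 example; both remain correct.
2. Say that 0.0508 and 0.732 belong to the fixed 5-of-67 test alone, and report the stopping probabilities of the rule actually used (with this clause, 25.8% at 3% and 83.6% at 9%).
3. State openly that one event in the first 8 patients still stops the trial. If the sponsor does not want that, requiring at least two events gives 11.9% and 78.3%. A different prior is also possible. Either change is a design choice and should come with the new boundaries and, where affected, a revised worked example.

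Items 1 and 2 cost a few sentences and leave the sample size and the table as they are. Item 1 changes one cell only, so no stop triggered by an event is lost. Item 3 costs nothing if the boundary is kept; relaxing it trades fewer false stops at 3% for less protection at 9%.

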IBRT	Ipsilateral Breast Tumor Recurrence
IBTR	Ipsilateral Breast Tumor Recurrence
IRB	Institutional Review Board
IMRT	Intensity Modulated Radiation Therapy
LFS	Local Recurrence-Free Survival
LR	Loco-regional
MR	Marginal Recurrence
NCI	National Cancer Institute
NIH	National Institutes of Health
NSABP	National Surgical Adjuvant Breast and Bowel Project

Accelerated, Hypofractionated Post-Mastectomy RT in Women with Breast Cancer: A Phase II Trial

OHRP	Office of Human Research Protection
OHRS	Office of Human Research Services
PBI	Partial Breast Irradiation
PD	Progressive disease
PHI	Protected Health Information
PI	Principal Investigator
PTV	Planning Target Volume
RL	Right-Left
RT	Radiation Therapy
RTOG	Radiation Therapy Oncology Group
RWJUH	Robert Wood Johnson University Hospital
SAE	Serious adverse event
TR	True Recurrence
TR/MM	True Recurrence/Marginal Miss
WBI	Whole Breast Irradiation

1. Purpose/Specific Objectives

1.1 Primary Endpoint:

The results from this novel fractionation scheme will be comparable to published locoregional control outcomes for conventionally fractionated chest wall irradiation.

- 1.1.1 Acute toxicity and late toxicity using previously published toxicity scales.

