The British Columbia trial enrolled 318 node-positive premenopausal breast cancer patients and randomized them after modified radical mastectomy to either radiation therapy or no additional locoregional therapy⁵⁰. Both groups received adjuvant CMF chemotherapy for 12 (first 80 patients) or 6 months. Radiation therapy was delivered to the chest wall to a dose of 37.5 Gy in 16 daily fractions through opposed tangential photon fields. The supraclavicular and axilla nodes were treated with an AP field and a posterior axillary field, as is conventionally done, with a target midaxilla dose of 35 Gy. Bilateral IMNs were treated with an additional anterior field to a dose of 37.5 Gy in 16 fractions. All treatments were delivered with cobalt machines, between cycle 4 and 5 of chemotherapy. After a median follow-up of 20 years, the 20-year survival free of locoregional disease developing before systemic was 61% in the chemotherapy alone arm and 87% in the irradiated group. The irradiated group had significantly higher 20-year event-free survival (25 vs 38%), systemic disease-free survival (31 vs 48%), breast-cancer specific survival (38 vs 53%), and overall survival (37 vs 47%). There were slightly more non-breast cancer deaths in the irradiated group (9% vs 4%, p=0.11). There were 3 cardiac deaths (2%) in the irradiated group versus one (0.6%) in the control group (p=0.62), and 9% of patients in the irradiated group developed arm edema compared with 3% in the control group (p=0.035).

The Early Breast Cancer Trialists' Collaborative Group has collected primary data from every randomized trial of adjuvant radiotherapy in breast cancer, and periodically reports the ongoing analyses on the benefits and risks of radiation therapy in these patients. The most recent report from 2005 reviewed data on 9933 patients enrolled on 25 trials of PMRT, all of which were unconfounded by the use of systemic therapy⁵³. Node-positive patients who had axillary clearance and received radiation therapy after mastectomy had a 5-year locoregional recurrence rate of 6%, compared to 23% for unirradiated controls (15-year rates were 8% vs 29%). In every large trial of PMRT in node-positive women, radiation therapy produced comparable proportional reductions in local recurrence in all women irrespective of age or tumor characteristics and regardless of time period--indeed a powerful demonstration of the efficacy of radiation therapy in reducing local recurrence.

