16.1 Primary and Secondary Hypotheses

The primary hypothesis of this study is that the delivery of hypofractionated, accelerated chest wall radiotherapy will result in toxicities will be similar to those reported for this patient population using standard of care postmastectomy radiation therapy.

The secondary endpoint is that locoregional control that is equal (non-inferior) to that reported for a conventional fractionation course of postmastectomy radiotherapy.

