21	0.125577	0.398811	0.682554	0.869637	0.957525	
22	0.114275	0.37422	0.657017	0.852799	0.949615	
23	0.10399	0.350825	0.631565	0.835179	0.940902	
24	0.094631	0.32861	0.606299	0.816854	0.931387	
25	0.086114	0.307552	0.581307	0.797904	0.921079	
26	0.078364	0.287622	0.556669	0.77841	0.909993	
27	0.071311	0.268789	0.532454	0.758453	0.89815	
28	0.064893	0.251016	0.508725	0.738113	0.885578	
29	0.059053	0.234265	0.485531	0.717468	0.872306	
30	0.053738	0.218496	0.462917	0.696594	0.858371	
31	0.048902	0.203668	0.440919	0.675563	0.843811	
32	0.044501	0.189739	0.419566	0.654445	0.828668	
33	0.040496	0.176667	0.398882	0.633306	0.812988	
34	0.036851	0.164412	0.378883	0.612208	0.796817	
35	0.033534	0.152931	0.35958	0.591209	0.780202	

We will use a fixed sample size of 67 patients, with locoregional recurrence rate as the secondary outcome of interest. For up to 5 recurrences out of 67 patients, we can say with 90% confidence that the true recurrence rate would be between 3.7% and 14.5%. We feel this is an acceptable level, and would be deemed non-inferior to previously reported recurrence rates.

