16.4 Outcome Measures

Time to local, regional, and/or distant failure will be recorded for primary endpoint analysis. Secondary endpoints will be measured by the data collected for toxicity as dichotomous variables; need for cosmetic reconstruction revision will also be collected and analyzed as a dichotomous variable.

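### Section 16.2 calls up to 5/67 locoregional recurrences non-inferior without a reference rate, time point or margin, and applies the interval for exactly 5 events to all lower counts

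*Combined protocol and SAP*

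**What the plan says.** Section 16.1 makes the secondary hypothesis "locoregional control that is equal (non-inferior) to that reported for a conventional fractionation course of postmastectomy radiotherapy". Section 1.1, under the primary endpoint heading, says the results will be "comparable to published locoregional control outcomes for conventionally fractionated chest wall irradiation". Neither gives a figure or a source.

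The only working criterion is in section 16.2. For up to 5 recurrences among 67 patients, "we can say with 90% confidence that the true recurrence rate would be between 3.7% and 14.5" per cent. The next sentence is the conclusion: "We feel this is an acceptable level, and would be deemed non-inferior to previously reported recurrence rates".

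Section 4.1 plans about 36 months of enrolment and a 72-month study, with at least 36 months of follow-up per patient. Section 16.5 plans life-table estimates of recurrence, but sets no landmark time and no comparison with an outside rate.

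**The concern.** A single-arm non-inferiority statement needs a reference rate, the time at which that rate applies, and a margin with a reason. Section 16.2 has none of these. Its justification is that the authors find the level acceptable. The criterion is also a crude count, with no time attached and no allowance for patients followed for different lengths of time.

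The interval adds a second difficulty. It is offered for any count up to 5, but a confidence interval belongs to one observed count.

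At stake is what the trial may say about disease control. Followed as written, 5 or fewer recurrences would let the shorter schedule be reported as non-inferior, although no reader could say to what rate or at what time. This matters beyond an ordinary secondary outcome because section 1.1 places locoregional control under the primary endpoint, while sections 16.1 and 16.2 treat it as secondary.

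**Working it through.** **1. Reproducing the interval.** Inputs from section 16.2: 5 events, n = 67, 90% confidence (z = 1.645, z² = 2.706). The Wilson score interval is

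[p + z²/2n ± z·√(p(1−p)/n + z²/4n²)] / (1 + z²/n)

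with p = 5/67 = 0.0746.

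- Centre: (0.0746 + 0.0202) / 1.0404 = 0.0911.
- Half-width: 1.645 × √(0.001031 + 0.000151) / 1.0404 = 0.0543.
- Limits: 3.68% and 14.55% (unrounded 14.548%, hence the printed 14.5%).

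Of the methods tried, only Wilson matches both printed limits; Clopper-Pearson, for example, gives 2.99% to 15.05%.

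**2. Fewer than 5 events.** Same formula:

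| Events | 90% Wilson interval |
|---|---|
| 5 | 3.7% to 14.5% |
| 3 | 1.8% to 10.7% |
| 0 | 0.0% to 3.9% |

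For counts up to 5, then, 14.5% is a ceiling on the upper limit, but 3.7% is not a floor on the lower one.

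**3. Possible reference rates.** Section 2.2 gives these for irradiated patients:

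- From the meta-analysis: "Node-positive patients who had axillary clearance and received radiation therapy after mastectomy had a 5-year locoregional recurrence rate of 6" per cent, and "15-year rates were 8% vs 29" per cent.
- From the two Danish trials: 9% at a median follow-up of 114 months and 8% at a median of 10 years. These are median follow-up times, not time points for the rate.
- From the British Columbia trial: "20-year survival free of locoregional disease developing before systemic was 61% in the chemotherapy alone arm and 87% in the irradiated group", so about 13% failure at 20 years. That trial gave 16 chest wall fractions.

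None is named as the benchmark. Only 6% at 5 years has an explicit time point inside this trial's 3- to 6-year follow-up. Even that rate is for node-positive patients with axillary clearance, whereas section 5.1.2 also admits sentinel biopsy alone and T3N0 or T4N0 disease. Against it, 14.5 − 6 = 8.5 points, and 14.5 / 6 = 2.4.

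**4. How often the rule passes.** A pass is 5 or fewer events in 67. Assumptions: follow-up uniform from 3 to 6 years (from section 4.1), no losses, and two hazard shapes to show the range. With r the true 5-year rate and H = −ln(1 − r), the risk by year t is

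F(t) = 1 − exp[−H·(t/5)^γ]

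- Constant hazard: γ = 1.
- Front-loaded hazard: the curve runs through 6% at 5 years and 8% at 15 years, so γ = ln(0.0834/0.0619) / ln 3 = 0.27.

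The mean risk is the average of F(t) over 3 to 6 years. The pass probability is the binomial P(X ≤ 5) with n = 67 at that mean risk.

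| True 5-year rate | Mean risk, front-loaded / constant | Pass probability, front-loaded / constant |
|---|---|---|
| 6% | 5.8% / 5.4% | 0.81 / 0.85 |
| 12% | 11.6% / 10.8% | 0.19 / 0.25 |

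A regimen with twice the 6% reference rate would still be called non-inferior about one time in five to one in four.

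**The case against.** The strongest reply is that section 16.2 only describes precision. On that view 14.5% is an upper confidence limit, not a declared margin, and no test is stated. Locoregional recurrence is secondary there, the 67 patients are sized on toxicity, and section 16.5 already plans life tables, so the final analysis need not be crude.

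Much of this stands. The interval is correctly calculated, 14.5% is nowhere called a margin, and a descriptive secondary outcome needs no power calculation. The rule's error can also be worked out once a bound is supplied: if the risk at the time of counting is 14.5%, the rule passes 6.4% of the time. But the text does not stop at description. It ends with a non-inferiority conclusion, and section 16.1 states that as a hypothesis. The life tables in section 16.5 are tied neither to a time point nor to a reference.

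A reader might go further and infer that the rule is badly underpowered. P(X ≤ 5) is 0.55 at a risk of 8% and 0.43 at 9%, and the implied margin would shrink to 6.5, 5.5 or even 1.5 points against 8%, 9% or 13%. The documents do not support that reading, because those rates come from about 10 to 20 years of follow-up and the trial counts events at 3 to 6 years. The 8% at 15 years lies on the same front-loaded curve as 6% at 5 years, for which the pass probability is 0.81. If the Danish 9% is assumed to be a 10-year rate, the method above gives 0.64 (front-loaded) to 0.94 (constant).

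**Conclusion.** The non-inferiority conclusion in section 16.2, and the matching hypothesis in section 16.1, are unsupported as written because reference rate, time point and margin are all missing. The printed interval is right for exactly 5 events and misdescribed for fewer.

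Set against the one early, dated rate in the background, the upper limit at 5 events is 8.5 points higher. The rule passes 81% to 85% of the time at a true 5-year rate of 6%, and 19% to 25% at 12%. These probabilities rest on the assumed uniform 36 to 72 months of follow-up, no losses and the two hazard shapes. The finding that the conclusion lacks support does not depend on them.

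The documents do not show that the interval is miscalculated, that 14.5% was adopted as a margin, or that the rule has poor power against the long-term rates.

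**What to change.** 1. In section 16.2, delete the non-inferiority conclusion. State that 3.7% to 14.5% is the 90% Wilson interval at exactly 5 recurrences, and that both limits are lower with fewer.
2. In section 16.1, replace the non-inferiority hypothesis with an objective to estimate locoregional recurrence. Make the comparability sentence in section 1.1 descriptive in the same way.
3. In section 16.5, specify the life-table estimate of locoregional recurrence at 36 months, which every patient still under observation should reach, and at 5 years as data allow, each with a 90% confidence interval.
4. If a non-inferiority claim is kept, name the reference rate at the same time point, give the margin and its reason, and state the rule's error and power. The documents give no 3-year reference rate, so one for 36 months would have to be sourced.

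The cost is wording in four sections. The sample size of 67 does not change. The sponsor gives up a non-inferiority statement that the plan does not support, or does the work of sourcing a reference and justifying a margin.
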